7.8.4. Baseline Descriptive Statistics

Summary statistics will be provided for all demographic and clinical characteristics (Section 7.6.1) for both before and after PS matching of patients to the 2 treatment cohorts (ABL and TPTD). (See Appendix 4 for the list of baseline comorbidities, prior medications, previous fractures, fall risk, and prior cardiovascular risks.) Numbers and percentages will be provided for dichotomous and polychotomous variables. Means, medians, standard deviations, will be provided for continuous variables.

7.8.5. Propensity Score Matching

In the absence of randomization, logistic regression-based PS matching will be used to create the analytic cohorts from all patients meeting the study inclusion/exclusion criteria. A greedy matching algorithm with no replacement will be adopted. The default caliper, the number of standard deviations of the distance measure within which to draw control unit, will be set at 0.20 (Austin et al, 2011). Additional sensitivity analyses using a tighter (0.15) or wider (0.3) caliper will be carried out. Cohorts will be prospectively specified to match on age, prior fracture history, osteoporosis-related hospitalization, and chronic comorbidities and concomitant medications during the pre-index period that are associated with an increased fall risk (see Appendix 1 for the full list of matching variables). The R software MatchIt package (<https://cran.r-project.org/web/packages/MatchIt/MatchIt.pdf>) will be used to find matched pairs. Pre-match and post-match will be evaluated using prespecified criteria for mean standard difference to ensure that PS matching was successful. After matching, the mean standard difference on each covariate between ABL and TPTD is expected to be < 0.10.

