- The primary effectiveness analysis will be an Intention-to-Treat (ITT) analysis.
- The primary safety analysis will be an As-Treated (AT) analysis.

Estimated Sample Size

Between May 2017 and June 2019, a total of 16,482 unique female patients ≥ 50 years of age treated with ABL and 45,350 unique patients ≥ 50 years of age treated with TPTD have been identified in the Symphony database. After applying inclusion/exclusion criteria, the final number of patients will be determined through PS matching. Based on previous studies, it is estimated that approximately 8,000 matched patients will be included in each cohort.

[figure not shown]

[figure not shown]
Sponsor Name: Radius Health, Inc.

Protocol Number: BA058-05-028

Protocol Version and Date: Original, V1.0, dated 09 July 2021

Page 27 of 63

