7.8.1. Power and Sample Size

7.8.1.1. Sample Size

All patients who meet the inclusion criteria and do not meet any of the exclusion criteria will be included in the analysis. After PS matching, it is estimated that approximately 16,000 patients will be included in the analyses, 8,000 patients in each cohort.

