7.8.1.2. Power Calculation

- Abaloparatide versus teriparatide with a noninferiority margin of 30%
 - Assuming a nonvertebral fracture rate of 3.5% at the end of 18 months
 - 8,000 matched subjects in each group
 - 95% power for HR up to 1.3

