7.8.6. Effectiveness Analyses

In this study, the primary analyses of effectiveness will be noninferiority analyses for ABL versus TPTD on time to the first incidence of nonvertebral fractures with a margin of 30%. Noninferiority of ABL to TPTD will be concluded if the upper bound of 2-sided 95% CI of HR between ABL versus TPTD is < 1.3.

In a recently published historical control observational study evaluating the real-world effectiveness of osteoporosis therapies using Medicare claim data between 2008 and 2011, the fracture incidence rates for the 12-month pre-treatment period were compared with the 12-month on-treatment period ([Yusuf et al, 2018](#)). For patients treated with TPTD, the incidence rate ratio (IRR [95% CI]) was 0.36 (0.31 to 0.41) for any fracture and 0.34 (0.32 to 0.36) for hip fracture. Based on the EMA and FDA noninferiority margin guidelines ([EMA, 2005](#); [FDA, 2016](#)), if the upper boundary of ABL versus TPTD is $HR < 1.3$, then ABL will preserve approximately 70% of the TPTD benefit, which is higher than the minimum required threshold of 50%.

Comparisons of the time to fracture between the PS-matched ABL and TPTD groups will be based on a Cox proportional hazards model. The hazard ratio (HR) and 95% confidence interval (CI) between the 2 treatment groups will be calculated. The Kaplan-Meier method will be used to estimate event rates. Log rank test will be calculated.

For the fracture outcomes, and the corresponding sensitivity and subgroup analyses, patients will be followed for up to 18 months or until their first fracture event (for the fracture site of interest under evaluation), whichever comes first. All analyses are based on index medication cohort.

The duration, in days, from the date of the first filled prescription for ABL or TPTD to the first incidence of nonvertebral fracture will be derived. If a patient does not experience any nonvertebral fractures during the 18 months of treatment + 30-day follow-up (for a total of 19 months), the patient will be censored at the day of in-hospital death or the 19 months.

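### Pair matching leaves any surplus of eligible teriparatide women unused, and the planned hazard-ratio test has about 87% power rather than the stated 95%; the plan does not report how large that surplus is

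*Combined protocol and SAP*

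**What the plan says.** Section 7.8.5 sets out logistic-regression propensity scores, a greedy algorithm without replacement and a caliper of 0.20. The R package "will be used to find matched pairs", and each covariate is expected to have a standardized difference below 0.10 after matching. No matching ratio is written, but pairs and equal cohort sizes imply 1:1. Section 7.8.1.1 expects that "approximately 16,000 patients will be included in the analyses, 8,000 patients in each cohort". Matching with more than one control per treated woman is not mentioned.

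The source pools are in Section 7.1, under the estimated sample size: "16,482 unique female patients ≥ 50 years of age treated with ABL and 45,350 unique patients ≥ 50 years of age treated with TPTD". That paragraph then says the final number follows from applying the eligibility criteria and matching.

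The power statement in Section 7.8.1.2 uses a 30% noninferiority margin and "8,000 matched subjects in each group". It reads "Assuming a nonvertebral fracture rate of 3.5% at the end of 18 months", and it claims "95% power for HR up to 1.3". Section 7.8.6 concludes noninferiority "if the upper bound of 2-sided 95% CI of HR between ABL versus TPTD is < 1.3", with the HR taken from a Cox model.

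**The concern.** Two things meet here. First, the TPTD pool as listed is 2.75 times the ABL pool, yet pair matching can use only one TPTD woman per ABL woman. If more eligible TPTD women lie within the caliper, pairing drops them, although their data come from the same single extraction. Second, the primary decision rests on the upper confidence limit of a hazard ratio, and the stated power does not appear to have been computed for that test. If true power is below 95%, unused controls are a ready source of extra events.

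At stake is a false failure to show noninferiority when the drugs are equivalent, and wider intervals for the sparse cardiovascular endpoints, which Section 7.8.3 analyses in the same matched population.

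**Working it through.** **Inputs.** Margin 1.3, event proportion 3.5% and 8,000 per group (7.8.1.2); upper limit of a 2-sided 95% CI, so one-sided 0.025 (7.8.6); pools 16,482 and 45,350 (7.1). The true HR is not stated and is taken as 1. ln 1.3 = 0.2624.

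**Step 1: reproduce the stated 95%.** Treat the endpoint as binary with a margin of 0.3 × 3.5% = 1.05 percentage points. SE = √(2 × 0.035 × 0.965 / 8,000) = 0.00291. Power = Φ(0.0105/0.00291 − 1.96) = 95.1%, and 95% power needs 7,962 per arm. This agrees with the plan, but on the risk-difference scale. Two other routes come within two points (642 events at one-sided 0.05, 95.3%; two proportions 3.5% v 4.55% at one-sided 0.05, 95.9%), but both contradict the 2-sided 95% CI rule. The plan shows no formula, so where its 95% came from is an inference.

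**Step 2: the planned HR test at 1:1.** Expected events are 280 per arm, 560 in all. SE(log HR) = √(1/280 + 1/280) = 0.0845. Power = Φ(0.2624/0.0845 − 1.96) = 87.4%. The largest observed HR that still passes is exp(0.2624 − 1.96 × 0.0845) = 1.10. At 1:1, 95% power needs 756 events, or 756/0.07 = 10,800 per group. Counting events to 19 months (591), as the 30-day extension in 7.8.6 allows, gives 89.0%.

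**Step 3: more TPTD matches, uniform ratio k.** SE = √(1/280 + 1/(280k)), with 8,000 ABL women throughout.

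| TPTD matched | k | Share of listed 45,350 | SE | Power | Largest passing HR |
|---|---|---|---|---|---|
| 8,000 | 1 | 17.6% | 0.0845 | 87.4% | 1.10 |
| 10,000 | 1.25 | 22.1% | 0.0802 | 90.5% | 1.11 |
| 12,000 | 1.5 | 26.5% | 0.0772 | 92.5% | 1.12 |
| 16,000 | 2 | 35.3% | 0.0732 | 94.8% | 1.13 |
| 22,000 | 2.75 | 48.5% | 0.0698 | 96.4% | 1.13 |

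The 95% level is reached at k = 2.07, about 16,560 matchable TPTD women (36.5% of those listed).

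**Step 4: unequal set sizes.** With matched-set weights the effective ratio is the harmonic mean of the set ratios. A mean of 2 made of half 1:1 and half 1:3 sets gives 1/(0.5/1 + 0.5/3) = 1.5, so 92.5%. A 30/40/30% mix of 1:1, 1:2 and 1:3 gives 1/(0.3 + 0.2 + 0.1) = 1.67, so 93.5%. An analysis stratified on matched set gives 93.5% and 94.0% for the same two mixes. Mean ratio 2 therefore means about 92.5% to 94.8%, the top figure being for exactly 1:2.

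**Step 5: is there a surplus?** Listed ratio: 45,350/16,482 = 2.75. If TPTD women survived eligibility and caliper at the ABL rate (8,000/16,482 = 48.5%), about 22,000 would be available. If only 17.6% did (8,000/45,350), there would be no surplus. The documents do not say where in that range the truth lies.

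**The case against.** The strongest objection is that the surplus is unproven. A reader might infer from 45,350 against 16,482 that pairing throws away most of the TPTD women: 17.6% of them used against 48.5% of ABL women. The documents do not support that. Both counts precede eligibility, so those percentages mix eligibility losses with matching losses. The loss is probably heavier for TPTD: Table 2 excludes prior anabolic users, and the synopsis dates TPTD's approval to 2002 and ABL's to 2017, so the TPTD count can include continuing users where the ABL count could have almost none when identification opened in May 2017. The TPTD count is also not labelled as women only. All of this stands, and any gain must be stated conditionally.

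A second tempting reading is that a variable-ratio match averaging two would restore 95%. It would not quite: Step 4 gives 92.5% to 94.0% for mixed set sizes.

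It can also be said that 1:1 caliper matching contradicts nothing in the plan, introduces no bias by itself and does not inflate the type I error, and that the mismatch in the power statement is a separate matter. That is fair. Pairing is not an error; it is a choice that may forgo precision. Later matches are also somewhat less close, and Section 7.1.3 already concedes that BMD, smoking and family history are unmeasured. The caliper and the 0.10 criterion limit the measured part of that cost; they cannot address the unmeasured part.

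**Conclusion.** The point holds in conditional form. Established: matching is in pairs without replacement, and the planned HR test has about 87% power at the plan's own inputs, not 95%. Not established: how many eligible, in-caliper TPTD women would go unused.

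Power with added matches therefore runs from 87% (no surplus), through about 92.5% to 94.8% at a mean ratio of 2, to about 96% at a uniform 1:2.75. At exactly 1:2 the chance of missing noninferiority when the true HR is 1 falls from 12.6% to 5.2%.

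These figures rest on a true HR of 1, 3.5% events in both arms, 8,000 matched ABL women, no loss other than the planned censoring, and a variance formula that treats the arms as independent. The case for extra matches is one of cheap precision, not of correcting a bias.

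**What to change.** 1. In 7.8.1.2, restate power as about 87% for the Cox HR test with 1:1 matching, and give the assumed true HR, the test level and the formula.
2. Before any outcome analysis, report eligible counts by arm. The flow diagram required by 7.8.2 can carry them.
3. In 7.8.5, write down the matching ratio. If a TPTD surplus exists, form the 1:1 matches first, so that the ABL women studied do not change, then add up to two further TPTD matches per ABL woman within the same 0.20 caliper. Use matched-set weights in the Cox, Kaplan-Meier and log-rank analyses, a variance clustered on the matched set, and the < 0.10 balance criterion on the weighted sample. Keep the 1:1 match as a sensitivity analysis.

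Cost: no new data, and a small change to the matching step. The larger effort is in weighted versions of the post-match baseline tables (7.8.4), the two caliper reruns (7.8.10.1) and the separately matched subgroups (7.8.11). Later matches will be slightly less close. If no surplus exists, the analysis stays 1:1 as planned, and only the power statement and the reported counts change.

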7.8.6. Effectiveness Analyses

In this study, the primary analyses of effectiveness will be noninferiority analyses for ABL versus TPTD on time to the first incidence of nonvertebral fractures with a margin of 30%. Noninferiority of ABL to TPTD will be concluded if the upper bound of 2-sided 95% CI of HR between ABL versus TPTD is < 1.3.

In a recently published historical control observational study evaluating the real-world effectiveness of osteoporosis therapies using Medicare claim data between 2008 and 2011, the fracture incidence rates for the 12-month pre-treatment period were compared with the 12-month on-treatment period ([Yusuf et al, 2018](#)). For patients treated with TPTD, the incidence rate ratio (IRR [95% CI]) was 0.36 (0.31 to 0.41) for any fracture and 0.34 (0.32 to 0.36) for hip fracture. Based on the EMA and FDA noninferiority margin guidelines ([EMA, 2005](#); [FDA, 2016](#)), if the upper boundary of ABL versus TPTD is $HR < 1.3$, then ABL will preserve approximately 70% of the TPTD benefit, which is higher than the minimum required threshold of 50%.

Comparisons of the time to fracture between the PS-matched ABL and TPTD groups will be based on a Cox proportional hazards model. The hazard ratio (HR) and 95% confidence interval (CI) between the 2 treatment groups will be calculated. The Kaplan-Meier method will be used to estimate event rates. Log rank test will be calculated.

For the fracture outcomes, and the corresponding sensitivity and subgroup analyses, patients will be followed for up to 18 months or until their first fracture event (for the fracture site of interest under evaluation), whichever comes first. All analyses are based on index medication cohort.

The duration, in days, from the date of the first filled prescription for ABL or TPTD to the first incidence of nonvertebral fracture will be derived. If a patient does not experience any nonvertebral fractures during the 18 months of treatment + 30-day follow-up (for a total of 19 months), the patient will be censored at the day of in-hospital death or the 19 months.

For the fracture outcomes, an ITT analysis will be applied. Patients will be followed for up to 18 months + 30-day follow-up, or until their first fracture event (for the fracture site of interest under evaluation) or in-hospital death, whichever comes first. Duration, in days, from the index date to the last follow-up date will be calculated. For calculation purposes, 1 month is equivalent to 30 days. All analyses are based on the patient's index medication cohort.

A nonvertebral fracture is any fragility fracture at the hip, pelvis, femur, ankle, shoulder (including shoulder, humerus, clavicle), radius/ulna, wrist, or tibia/fibula. Derivation details are provided in [Appendix 2](#).

The time to the first incidence of hip fracture and the other 7 individual fracture sites will be summarized using similar methods as those used for nonvertebral fracture.

The Kaplan-Meier curves will be generated to graphically display the fracture event or 18 months plus 30-day follow-up.

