Spinal fractures have also been associated with poor outcomes and high mortality rates (Suzuki et al, 2008). It has been reported that once a patient has sustained a vertebral fracture, the risk of a subsequent vertebral fracture increases by > 300% and the risk of a subsequent hip fracture increases by 200% (Black et al, 1999). Additional studies have shown that almost half of patients with a prior vertebral fracture will experience additional vertebral fractures within the next 3 years, many within the first year (Robinson et al, 2002; Lindsay et al, 2001). Patients who sustained a vertebral body fragility fracture had a prolonged course, which can lead to significant disability even 1 year later (Suzuki et al, 2008). Patients with a diagnosis of osteoporosis who have experienced any fracture have an 86% increase in their risk for another fracture (Kanis et al, 2004). With the severity of these implications, prevention of subsequent fractures has become a primary focus from a patient care and societal standpoint.

Major osteoporotic fractures (those of the wrist, shoulder, hip, and clinical spine) account for 94% of the fracture risk for women with low or minimal trauma (Ensrud et al, 2016). Major osteoporotic fractures contribute to accumulated frailty such that the Frailty Index is significantly higher in those elderly women who have experienced a major osteoporotic fracture. As a result, these women have worsening frailty and greater morbidity after a major osteoporotic fracture (Li et al, 2016). The Frailty Index was associated with a predicted increase in the risk of falls, fractures, death, and overnight hospitalizations (Li et al, 2014). Consequently, prevention of clinically significant and medically relevant major osteoporotic fractures has the potential to reduce health care costs, and reduce the risk of falls, fractures, hospitalizations, and death as well as benefit postmenopausal women based on reduced frailty.

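### No covariates or pair-level variance are named for the primary Cox model, so imbalance that the matching criterion tolerates could pass uncorrected into the noninferiority decision

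*Combined protocol and SAP*

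**What the plan says.** Section 7.8.6 states the primary analysis model: "Comparisons of the time to fracture between the PS-matched ABL and TPTD groups will be based on a Cox proportional hazards model". Noninferiority is concluded if the "upper bound of 2-sided 95% CI of HR between ABL versus TPTD is < 1.3". Neither that section nor the safety analysis in section 7.8.7 names covariates, strata, a robust variance or any use of the pairs.

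Section 7.8.5 builds the cohorts by greedy propensity score matching without replacement, with a caliper of 0.20, and produces matched pairs. The balance target is an expectation: "After matching, the mean standard difference on each covariate between ABL and TPTD is expected to be < 0.10". No action is attached to a variable that misses it or comes close.

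The planned variations are other calipers (0.15 and 0.3, section 7.8.10.1) and subgroups that are each matched afresh (section 7.8.11). Section 7.1.3 concedes that confounding may remain after matching, but no analysis is tied to that remark.

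On the strength of one matching variable, section 6.1 says that patients with osteoporosis who "have experienced any fracture have an 86% increase in their risk for another fracture". Section 7.8.11 treats fracture history as the strongest predictor of later fracture.

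**The concern.** The whole primary conclusion rests on whether one confidence limit lies below 1.3. With about 560 events the standard error of the log HR is near 0.085, so a 3% bias is worth nearly 0.4 standard errors. Imbalance in a strong predictor can produce a bias of that size while the plan's balance check is still met, and nothing in the primary analysis would take it out.

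The exposure runs both ways. If the abaloparatide cohort had fewer prior fractures, an inferior drug would pass too often. If it had more, a truly equivalent drug would fail more often than planned.

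The silence also matters in itself. The data are retrospective, and a model whose terms are not fixed in advance leaves the covariate set open.

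**Working it through.** **Inputs from the documents.** Margin 1.3 with a two-sided 95% interval (7.8.6). "Assuming a nonvertebral fracture rate of 3.5% at the end of 18 months" and "8,000 matched subjects in each group" (7.8.1.2), which give 2 × 8,000 × 0.035 = 560 events. Risk ratio 1.86 for prior fracture (6.1). Standardised difference limit 0.10 (7.8.5).

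**Assumptions.** The documents give no prevalence of prior fracture, so 20-40% is assumed, with a wider range below. The event count is taken as 560, or 640 to allow for a higher rate in one arm: 280 + 280 × 1.3 = 644 if the abaloparatide arm is at HR 1.3. The 86% figure is for any fracture. Using it for nonvertebral fracture over 18 months is also an assumption.

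**The plan's own power figure.** Section 7.8.1.2 claims "95% power for HR up to 1.3". This reproduces as a risk-difference calculation. The margin is 0.3 × 3.5% = 1.05 points and the SE is √(2 × 0.035 × 0.965 / 8,000) = 0.00291, so power is Φ(0.0105/0.00291 − 1.96) = 95.1%. On the planned HR scale, with 560 events, it is Φ(ln 1.3 × √140 − 1.96) = Φ(1.144) = 87.4%. The 87% is the baseline used here, because the decision is made on the HR.

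**Bias from prior fracture.** Let p_T and p_A be the prevalences in the teriparatide and abaloparatide cohorts. The unadjusted log HR is too low by

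b = ln[(1 + 0.86 p_T) / (1 + 0.86 p_A)].

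At an average prevalence of 30% and a standardised difference of 0.10, p_T = 0.323 and p_A = 0.277 (4.6 points apart). Then b = ln(1.2777/1.2383) = 0.0313, a factor of 1.032.

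**False noninferiority rate at true HR 1.3** = Φ(−1.96 + b√(events/4)).

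- 560 events: Φ(−1.96 + 0.0313 × 11.83) = Φ(−1.590) = 5.6%.
- 640 events: Φ(−1.96 + 0.0313 × 12.65) = Φ(−1.564) = 5.9%.

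By size of imbalance (risk ratio 1.86, 560 events):

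| Standardised difference | 20% prevalence | 30% | 40% |
|---|---|---|---|
| 0.016 | 2.8% | 2.9% | 2.9% |
| 0.05 | 3.7% | 3.8% | 3.8% |
| 0.085 | 4.8% | 5.0% | 5.0% |
| 0.10 | 5.3% | 5.6% | 5.6% |

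With 640 events the bottom row is 5.6%, 5.9% and 5.9%. The first row is the chance level: the SD of a standardised difference with 8,000 per arm is √(2/8,000) = 0.016. Outside the 20-40% range, a difference of 0.10 with 560 events gives 4.0% at 5% prevalence, 4.7% at 10%, 5.1% at 60% and 4.8% at 70%.

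**Opposite direction** (30% prevalence, difference 0.10, 560 events). Power at HR 1 is Φ((0.2624 − 0.0313) × 11.83 − 1.96) = Φ(0.774) = 78%, against 87% with no imbalance. The false noninferiority rate falls to about 1.0%.

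**Does adjustment cure it?** A simulation of 12,000 runs per setting, with an exponential rate model standing in for the Cox model, used 30% prevalence and a difference of 0.10. The false noninferiority rate was 6.1% with treatment alone and 2.7% with prior fracture in the model. At zero imbalance both were 2.5%.

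**Pairing.** With a between-pair SD s of log risk, the within-pair correlation is about 0.035 × (exp(s²) − 1), and the correct SE is √(1 − correlation) times the unpaired one. That ratio is 0.998 for s = 0.3 and 0.970 for s = 1.0. Ignoring the pairs makes the interval about 0.2-3% too wide.

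**The case against.** The strongest reply is that a difference near 0.10 on prior fracture is unlikely. Prior fracture is itself a matching variable. By chance alone, 0.085 would be more than five SDs (0.085/0.016 = 5.3), so it would have to come from poor matching. Section 7.1 counts 45,350 teriparatide users against 16,482 abaloparatide users before eligibility, for about 8,000 pairs, and section 6.3 reports that new users of the two drugs had similar disease characteristics. This stands: the 5-6% figure is a limit, not a forecast.

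It can also be said that the plan has related safeguards. Balance is tabulated after matching, a tighter caliper is tried, and effectiveness subgroups by age, prior bisphosphonate use and fracture in the previous year are matched separately. These would help a reader judge the result. But a tighter caliper changes closeness on the propensity score rather than adjusting for one predictor, and re-matched subgroups do not correct the primary HR on which noninferiority is declared.

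Relying on matching alone is a coherent design choice. If that is what is meant, the plan should say so. Even then, adjustment for strong predictors is a better guard at almost no cost.

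Two stronger readings are tempting. A reader might infer that the plan commits to a treatment-only model. It does not say that; it leaves the terms unstated. A reader might also infer that ignoring the pairs raises the error rate. The arithmetic shows the reverse: the interval becomes slightly conservative.

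**Conclusion.** The point holds as a gap in specification with a bounded consequence. The primary decision rests on a Cox model with no named covariates and no account of pairs, and no planned analysis adjusts the primary HR for imbalance left by matching. If the model contains treatment alone and prior fracture is imbalanced in abaloparatide's favour near 0.10, the bias is about 3% and the false noninferiority rate about 5-6% instead of 2.5%. This rests on a risk ratio of 1.86, an assumed prevalence of 20-40% and 560-640 events. With 560 events, doubling the error needs a difference of about 0.085 or more at 30-40% prevalence. At 0.05 the rate is about 3.8%, and at chance level about 2.9%. In the opposite direction, power at HR 1 falls from about 87% to about 78%.

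The documents do not support a claim that the error rate will double. They give neither the prevalence nor any sign that imbalance will lie near the limit. The change is worth making because it is cheap and removes the exposure in both directions.

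**What to change.** State in section 7.8.6 that the primary Cox model includes treatment, age, prior fracture and prior osteoporosis treatment, plus any matching variable whose standardised difference misses the plan's own 0.10 criterion after matching. In section 7.8.7, state the same for the safety models and add prior myocardial infarction, stroke and heart failure. Use a robust variance clustered on matched pair throughout. Report the treatment-only model as supportive.

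The cost is a few model terms and a slightly longer SAP. These variables are already planned for extraction or matching (sections 7.6.1, 7.6.2, 7.6.4 and 7.8.5), so no new data are needed. With a 3.5% event rate the adjusted and unadjusted HRs estimate practically the same quantity, so the 1.3 margin keeps its meaning.
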